8.5 Statistical Analyses of Efficacy

Categorical variables will be summarized with the number and percent of subjects in each treatment group with the characteristic. Quantitative variables will be summarized with the mean, median, standard deviation, minimum value, and maximum value. Baseline will be defined as the last value obtained before randomization.

Phase I

The treatment differences for the changing IRLSS score from Baseline to Day 42 will be assessed with the analysis of covariance with treatment as a fixed effect and baseline value as a covariate.

The treatment difference for the percentage of subjects who are much or very much improved at Day 42 as measured by the CGI-I will be assessed with the chi-square test.

Change from Baseline for IRLSS at Day 28, MOS at Day 42, and brain iron distribution at Day 42 will be assessed with the same method as IRLSS at Day 42. The percentage of subjects who are much or very much improved at Day 42 as measured by the PGI-I will be assessed with the chi-square test.

Phase II and III

All analyses will be descriptive.

For Phase II, the proportion of treatment **Non-Responders** in Phase I who respond to FCM in Phase II will be estimated and the IRLSS, CGI-I, PGI-I and brain iron distribution will be summarized at Day 42.

The Kaplan-Meier method will be used to estimate time from first dose of FCM to treatment intervention. Subjects in Phase III who discontinue the study before requiring treatment intervention will be censored on the day of the last contact with the Investigator.

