1. INTRODUCTION

The purpose of this statistical analysis plan (SAP) is to describe the procedures and the statistical methods that will be used to analyze and report results for Protocol 1VIT15042 (Date: 4 September 2019). This SAP should be read in conjunction with the study protocol and case report forms (CRFs).

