1.2 STUDY ENDPOINTS

1.2.1 Primary Efficacy Endpoint(s)

Primary efficacy endpoint in **Treatment Phase I** is to determine the effectiveness of FCM in improving RLS severity associated with IDA. Effectiveness will be evaluated by:

- IRLSS score change from baseline to Day 42 with comparison between FCM vs. Placebo.
- CGI-I at Day 42.

Primary efficacy endpoint in **Treatment Phase II** is to determine the effectiveness of an additional unblinded single FCM treatment in improving RLS severity in non-responders from Treatment Phase I. Effectiveness will be evaluated by:

- IRLSS score change from baseline (For Phase II the “baseline” is established on Day 42 of Phase I) compared to Day 42 of Treatment Phase II
- CGI-I at Day 42 in Treatment Phase II.

Primary efficacy endpoint in **Long-Term Extension Phase III** is to evaluate the duration of effect of FCM as defined as the number of weeks from the initial treatment without need for further treatment. Initial treatment is defined as Day 0 of Phase I for Responders in Phase I and Day 0 of Phase II for Responders in Phase II.

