2.4 HANDLING OF MISSING DATA

Missing data will not be imputed for descriptive statistical summaries in safety or efficacy analyses.

For the PGI-I score, missing data at Day 42 will be considered as failure in analysis.

Dates missing the day or both day and month of the year will adhere to the following conventions to classify TEAE and to classify prior/concomitant medications.

- A medication with a completely missing start date will be considered a prior medication. A medication with a completely missing stop date will be considered a concomitant medication.
- If complete AE onset date is missing and AE end date is on or after the first dose date then it will be counted as a treatment emergent AE (TEAE) for the study. If complete AE onset date is missing and AE end date is before the first dose date then it will be counted as a not treatment emergent AE (TEAE) for the study.
- If an AE or a medication has a partial missing start or stop date, the following rules will be used for imputation:
 - If year is present but month and day are missing, impute start date as January 1 of that year or first dose date if the year is the same as the year of first dose date and impute stop date as December 31 of that year.
 - If year and day are present but month is missing, impute start month as January or the month of the first dose date if the year and day is the same as the year and day of first dose date and impute stop month as December.
 - If year and month are present but day is missing, impute start date as first day of that month or first dose date if the year and month are the same as the year and month of first dose date and impute stop date as last day of that month.

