5. STUDY DRUG AND EXPOSURE

5.1 TREATMENT COMPLIANCE AND EXTENT OF EXPOSURE

Treatment compliance will not be summarized, as each subject will be treated in an inpatient setting to receive a single dose of study drug on Day 0 and Day 7 of Phase I or II or a single dose during any time before week 46 of Phase III.

The number (percentage) of subjects who received IV injections of study drug will be summarized by treatment phase, treatment group (for Phase I only) and overall for safety population. The number (percentage) of subjects who received additional IV injection of study drug in Phase III will be summarized for Phase III safety population.

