6.1.3 Phase III: Time from initial FCM treatment to further FCM treatment

Time (weeks) from the initial FCM treatment to further FCM treatment received in Phase III will be calculated as the integer of $(\text{date of the further FCM treatment in Phase III} - \text{date of the initial FCM treatment}) / 7 + 1$. The time duration will be summarized via descriptive statistics including number of subjects, median, minimum (min) and maximum (max). Initial treatment is defined as Day 0 of Phase I for responders in Phase I and Day 0 of Phase II for responders in Phase II. At any time before week 46 subject could receive a single dose of unblinded FCM treatment (i.e. the further FCM treatment) if RLS symptom is worsened.

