9. SUMMARY OF MAJOR CHANGES IN THE PLANNED ANALYSES

Compared with the study protocol 1VIT15042 (Date: 4 September 2019), below items are the major changes made in this SAP:

1. Due to early termination of the study, no statistical analysis will be performed. Hence no primary, and secondary end points will not be tested with statistical model.
2. Physical examinations was removed from safety analysis list and any significant findings will go to medical history or adverse event summaries.
3. The secondary endpoint “Number of Subjects who remained in the study to Week 52” will be summarized in disposition table for n (%) of study completer. It will not be considered as an efficacy endpoint in this SAP.
4. Adverse events of special interest were added in this SAP in Section 7.1.1.

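### SAP 6.1.3 summarises time to further FCM only among Phase III responders who were re-dosed, so the median generally understates duration of effect

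*SAP*

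**What the plan says.** SAP 1.2.1 defines the Phase III primary endpoint as the "number of weeks from the initial treatment without need for further treatment". The clock starts at Day 0 of Phase I for Phase I responders and Day 0 of Phase II for Phase II responders.

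SAP 6.1.3 puts this into practice as follows: "Time (weeks) from the initial FCM treatment to further FCM treatment received in Phase III will be calculated" as the integer of the date difference divided by 7, plus 1. Then: "The time duration will be summarized via descriptive statistics including number of subjects, median, minimum (min) and maximum (max"). No rule covers a responder without a further dose. SAP 2.4 adds: "Missing data will not be imputed for descriptive statistical summaries in safety or efficacy analyses".

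Two other parts of the SAP bear on this. SAP 5.1: "The number (percentage) of subjects who received additional IV injection of study drug in Phase III will be summarized for Phase III safety population". SAP section 9: "Due to early termination of the study, no statistical analysis will be performed".

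Section 8.5 of the supplied Protocol says of Phases II and III: "All analyses will be descriptive". Under that same statement it specifies Kaplan-Meier for time from first FCM dose to treatment intervention, censoring those who discontinue before intervention at their last contact.

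**The concern.** The endpoint concerns every responder who enters Phase III, but the calculation yields a number only for those whose effect was lost and who were then re-dosed. A responder still well at Week 52 has the best possible outcome and contributes nothing. The same holds for responders who withdrew, were lost, or were cut off when the study ended early. The SAP does not state this exclusion in words. It follows from the formula (no re-dose date, no value) together with the no-imputation rule.

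A clinical reader would take the printed median as how long FCM works in this population. It answers a different question: among those re-dosed within the permitted window, how soon did that happen? Phase III is uncontrolled and untested, so what is at stake is a misleading descriptive duration for a primary endpoint.

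**Working it through.** The documents state no expected duration, relapse rate or sample size for Phase III, so there is no plan figure to reproduce.

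**1. Ceiling (from the documents).** Value = integer part of (days/7 + 1).
- Phase I responders. SAP 1.3.1 allows no dose after Week 46: day 322 gives 322/7 + 1 = 47. SAP 6.1.3 says before week 46: day 321 gives 46.86, so 46.
- Phase II responders. Phase II Day 0 falls within 7 days of the Day 42 visit, which has a +3 day window, so on day 42 to 52. Day 322 is then 280 to 270 days later: 280/7 + 1 = 41 and 270/7 + 1 = 39.57, so 39.

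**2. Illustration (assumed rates).** Assume a constant hazard of losing effect after Week 6, with every loss re-dosed. As a rough anchor, the iron dextran pilot in the Protocol introduction reports that one-third of responders were not sustained beyond six months. That is a different product and dose, so it is only a guide.
- Rate: S(26) = 2/3, so ln(1.5)/20 = 0.0203 per week.
- True median: 6 + ln(2)/0.0203 = 40.2 weeks.
- Re-dosed by Week 46: 1 − exp(−0.0203 × 40) = 1 − 0.444 = 55.6%.
- Median among the re-dosed: 6 − ln(1 − 0.5 × 0.556)/0.0203 = 22.1 weeks, printed as 23.

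The same steps with other true medians, for Phase I responders:

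| True median (weeks) | Still free at Week 46 | Median among re-dosed | SAP prints |
|---|---|---|---|
| 32 | 34.4% | 20.9 | 21 |
| 40.2 | 44.4% | 22.1 | 23 |
| 58 | 58.7% | 23.4 | 24 |

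True durations 26 weeks apart (58 − 32) give printed medians 3 weeks apart (24 − 21). In the last row Kaplan-Meier would read 'not reached'. As the hazard tends to zero, re-dose times become uniform over Weeks 6 to 46, so the conditional median tends to 6 + 20 = 26, or 27 with the +1. For Phase II responders, with 33-34 weeks of eligibility, the anchor case prints 20-21.

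**3. Other shapes.** A simulation of 400,000 subjects per setting used Weibull shapes 0.7, 1 and 1.5, 20-90% re-dosed by Week 46, and 0 or 20% dropout. In all 42 settings the SAP median was below the true median. For constant hazard without dropout:

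| Re-dosed by Week 46 (assumed) | True median | Kaplan-Meier median | SAP prints |
|---|---|---|---|
| 20% | 130 | not reached | 25 |
| 50% | 46 | at or beyond Week 46 | 23 |
| 70% | 29 | 29 | 21 |
| 90% | 18 | 18 | 17 |

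The gap nearly closes when almost everyone is re-dosed.

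**4. Early termination.** If follow-up ended evenly between Weeks 6 and 46, the printed medians for true medians of 32, 40.2 and 58 weeks fall to 16, 16 and 17 (simulated).

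**5. Can the direction reverse?** Yes. Take a true median of 18 weeks (rate ln(2)/12 = 0.0578) and suppose the laboratory criteria bar re-dosing in 80% of losses before Week 18 and 10% after.
- Re-dosed before Week 18: 0.5 × 0.2 = 0.10.
- Re-dosed from Week 18 to 46: (0.5 − 0.099) × 0.9 = 0.361.
- Half of the total 0.461 is reached at 23.9 weeks, printed as 24, which is above 18.

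**6. What Kaplan-Meier on re-dosing alone leaves out.** At the anchor, 0.444 are truly free at Week 46. If 10-20% of losses cannot be re-dosed (assumed) and those subjects leave, the curve gives 0.444^0.9 = 0.48 to 0.444^0.8 = 0.52. If they stay, it gives 1 − 0.9 × 0.556 = 0.50 to 1 − 0.8 × 0.556 = 0.56. The number of such subjects is therefore needed beside the curve.

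**The case against.** **Early termination justified plain summaries, and the SAP says so.** SAP sections 6 and 9 announce descriptive statistics only. This stands as a reason for dropping tests and models. It does not justify dropping censoring. A Kaplan-Meier curve without a test is descriptive, and Protocol 8.5 classes it so. Termination adds incomplete follow-up, which makes censoring more necessary.

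**The omitted subjects are visible elsewhere.** SAP 5.1 gives the share re-dosed, SAP 6.2.10 summarises IRLSS (symptom severity) scores through Week 52, and disposition counts completers. A careful reader could see what share the median describes. None of these corrects the median.

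**The ceiling is a feature of the design.** This is right. A Kaplan-Meier median for re-dosing cannot lie beyond Week 46 either. The difference is that Kaplan-Meier would say the median was not reached.

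**Three stronger readings are tempting.**
- A reader might infer that the SAP abandoned a binding Kaplan-Meier commitment. This cannot be shown. The SAP says it will "analyze and report results for Protocol 1VIT15042 (Date: 4 September 2019"), and that version was not supplied. The supplied Protocol carries April 2016 dates. The point rests on the mismatch between SAP 1.2.1 and SAP 6.1.3.
- A reader might infer that worsening without re-dosing, or a switch to other RLS therapy, must count as an event. The wording about need for treatment invites this, but Protocol 8.4.1, Protocol 8.5 and SAP 6.1.3 all time FCM treatment alone.
- A reader might infer that the median is always too short. Step 5 of the working shows an exception.

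**Conclusion.** The concern holds. The SAP 6.1.3 median is conditional on re-dosing and does not estimate the Phase III primary endpoint as SAP 1.2.1 defines it. It generally understates duration of effect. The exceptions are near-complete re-dosing, where the shortfall almost vanishes, and ineligibility for re-dosing concentrated among early relapses, where the direction can reverse.

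Only the ceilings follow from the documents: 46-47 weeks for Phase I responders and 39-41 for Phase II responders. The size of the shortfall (for example 23 printed against about 40 true) rests on an assumed constant hazard and a borrowed anchor, and is illustration only.

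The consequence is limited to one descriptive result in an uncontrolled phase; no test is affected. It should still be corrected, because this is the only planned summary of that phase's primary endpoint.

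**What to change.** In SAP 6.1.3, replace the present summary with a descriptive Kaplan-Meier estimate of time to FCM re-dosing over all Phase III responders. Censor those never re-dosed at last contact, as in section 8.5 of the supplied Protocol. Do not read the curve past the Week 46 dosing limit, since no event can occur after it.

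Show Phase I placebo responders separately. SAP 6.1.3 starts their clock at Phase I Day 0, when they received saline, so their time is not a duration of FCM effect.

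Beside the curve, report how many responders left for other RLS therapy and how many worsened but could not be re-dosed. A composite event that includes them is an optional sensitivity analysis.

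At minimum, keep the present median, label it 'among re-dosed subjects', and print the number of Phase III responders next to it.

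The cost is one SAP paragraph and one extra descriptive output from data already collected. Dosing rules do not change. In a terminated study the median may not be reached; if so, that is the correct result to report.

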26. APR 2016

Date

Date

27 17 pr. 1 2016 Date

28 April 2016 Date

STUDY SYNOPSIS

Protocol 1VIT15042

Title: Randomized, placebo-controlled trial of ferric carboxymaltose in Restless Legs Syndrome patients with iron-deficiency anemia

Investigational Drug: Injectafer® (Ferric Carboxymaltose - FCM)

Treatment Phase I and II Primary Objective: To evaluate the efficacy and safety of FCM (750 mg dose x 2) for treatment of Restless Legs Syndrome (RLS) in patients with irondeficiency anemia (IDA).

Long-Term Extension Phase III Primary Objective: To evaluate the duration of effect of prior FCM treatment and to determine the effectiveness of further iron repletion with FCM when RLS symptoms worsen or reoccur.

Study Design: This will be a Phase II, randomized, placebo-controlled study. All subjects who meet the inclusion criteria, with no exclusion criteria, will qualify to enter the Screening Phase. The study will enroll 70 eligible subjects to receive blinded study drug in Treatment Phase I. All eligible subjects will be randomized in a 1:1 ratio to receive a blinded dose of either FCM 750 mg undiluted slow intravenous (IV) push at 100 mg/minute or a Placebo (15 ml of Normal Saline [NS]) IV push at 2 ml/minute on Day 0 and 7.

A subject will be defined at Day 42 as a **Responder** if the International Restless Legs Syndrome Severity Scale (IRLSS) score is ≤ 10 or if the IRLSS score is >10 with a Clinical Global Impression-Improvement (CGI-I) score of much or very much improvement and the subject does not request further treatment for RLS. A subject will be defined as a treatment **Non-Responder** if neither of these criteria are met.

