Primary efficacy endpoint in **Long-Term Extension Phase III** is to evaluate the duration of effect of FCM as defined as the number of weeks from the initial treatment without need for further treatment. Initial treatment is defined as Day 0 of Phase I for Responders in Phase I and Day 0 of Phase II for Responders in Phase II.

Secondary object is to determine the effectiveness (number of subjects who remain in the study) of additional FCM treatment, in the Long-Term Extension, in those who have worsening of RLS symptoms after the initial response.

Primary safety endpoint is to determine the safety of FCM in RLS patients with IDA

- Safety Evaluations will include:
 - Adverse events
 - Laboratory assessments, including hematology (Hgb, Hct, RBC, WBC, MCV, MCH, MCHC, RDW, platelets, differential count), iron indices (serum iron, serum ferritin, and total iron binding capacity (TIBC), percentage serum transferrin saturation (TSAT)), clinical chemistry (sodium, potassium, chloride, BUN, creatinine, albumin, alkaline phosphatase, total bilirubin, gamma-GGT, AST, ALT, LDH, calcium, phosphorus, glucose, bicarbonate)
 - Vital signs
 - Physical examinations.

Exploratory Aims:

- 1. Evaluate potential predictors of Day 42 (Treatment Phases I and II) treatment response using clinical, hematologic, and brain MRI data.
- 2. The change from baseline in MRI-determined iron concentration for other brain regions.
- 3. Correlation between changes in brain iron distribution and measures of peripheral iron status, RLS severity, and sleep quality.

- 4. Correlation between CBC, iron indices, and change from Baseline to Day 42 (Treatment Phases I and II) RLS severity, sleep, and PGI-I.
- 5. Correlation of baseline Vitamin D and post dose change in phosphate.
- 6. Vitamin D at each visit.

Inclusion Criteria:

- 1. Male or female subject ≥ 18 years of age who is able to give informed consent.
- 2. Confirmed diagnosis of RLS based on the Cambridge-Hopkins Diagnostic Questionnaire (CHDQ) and the Hopkins-Hening Telephone Diagnostic Interview (HDTI).
- 3. IRLSS score \geq 15 plus RLS symptoms for at least 3 months and currently occurring \geq 2 nights per week.
- 4. Iron-deficiency anemia defined as an Hgb <12 g/dl with a ferritin <20 ng/mL, or ferritin <100 when TSAT is <18%.
- 5. Subjects on sleep medication must be on a stable dose for at least 6 months prior screening.

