8.4 Endpoints and Definitions

8.4.1 Primary Endpoints

Treatment Phase I co-primary endpoints are:

- Change in IRLSS score from Baseline to Day 42 with comparison between FCM vs. Placebo, and
- Percentage of subjects who are much or very much improved at Day 42 as measured by the CGI-I.

Treatment Phase II primary efficacy endpoints are:

- IRLSS score change from Baseline (For Phase II the "baseline" is established on Day 42 of Phase I) compared to Day 42 in phase II.
- CGI-I at Day 42 in Treatment Phase II.

Long-Term Extension Phase III primary efficacy endpoints are:

• Estimate the time from first dose of FCM (Day 0 in either Phase I or Phase II) to time of FCM treatment intervention.

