1.1 STUDY OBJECTIVES

1.1.1 Primary Objective(s)

Treatment Phases I and II primary objective is to evaluate the efficacy and safety of FCM (750 mg dose x 2) for treatment of Restless Legs Syndrome (RLS) in patients with iron-deficiency anemia (IDA).

Long-term extension Phase III primary objective is to evaluate the duration of effect of prior FCM treatment and to determine the effectiveness of further iron repletion with FCM when RLS symptoms worsen or reoccur.

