1.3 SUMMARY OF THE STUDY DESIGN

1.3.1 General Study Design and Plan

This is a Phase II, randomized, placebo-controlled multi-center study to evaluate the efficacy and safety of Injectafer® (FCM Injection) for treatment of Restless Leg Syndrome (RLS) with iron-deficiency anemia (IDA).

FCM is a stable Type I polynuclear iron (III)-hydroxide carbohydrate complex developed as an intravenous (IV) iron replacement therapy for the treatment of IDA¹. All subjects who meet the inclusion requirements and no exclusion criteria will qualify to enter the screening phase. The study will include 3 treatment phases, i.e. Phase I (42 days), II (42 days) and III (46 weeks long-term extension), and will enroll 70 subjects to be randomized into Treatment Phase I.

In **Treatment Phase I**, all eligible subjects will be randomized in a 1:1 ratio to receive a blinded dose of either FCM 750 mg undiluted slow IV push at 100 mg/minute or a Placebo (15 ml of Normal Saline) IV push at 2 ml/minute on Days 0 and 7. At the end of treatment Phase I (i.e. Day 42), all subjects will be defined as either treatment responders or non-responders defined as:

Responder: IRLSS total score ≤ 10 , or IRLSS total score > 10 with a CGI-I score of much or very much improvement and the patient does not request further treatment for RLS.

Non-Responder: if neither of these above criteria are met.

In **Treatment Phase II**, Treatment Phase I Non-Responders who have met the necessary laboratory criteria (ferritin < 300 ng/mL and a TSAT $< 45\%$) will be consented for enrollment in Treatment Phase II. Day 0 of treatment Phase II will occur within 7 days of the completing Treatment Phase I Day 42 visit. These subjects will receive an unblinded 750 mg dose of FCM, treatments will be given as an undiluted slow IV push at 100 mg/minute on Days 0 and 7 of Phase II consequently. Treatment Phase I Non-Responders who do not meet the laboratory criteria for additional dosing will be discontinued from the study and treated for RLS as deemed appropriate by the referring physician. Subjects completing Treatment Phase II will be re-evaluated on Day 42 and defined as either a Responder or Non-Responder, using the same criteria described above. Treatment Phase II Non-Responders will be discontinued from the study after final assessments are complete.

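### SAP 6.1.3 is inconsistent about Phase I placebo responders: its title and formula need an earlier FCM date, but its definition sentence gives every Phase I responder Phase I Day 0

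*SAP*

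**What the plan says.** - **Objective.** SAP 1.1.1 gives the Phase III aim as to "evaluate the duration of effect of prior FCM treatment". The protocol synopsis has the same aim.
- **Endpoint.** SAP 1.2.1 intends to "evaluate the duration of effect of FCM as defined as the number of weeks from the initial treatment without need for further treatment".
- **Calculation.** SAP 6.1.3 subtracts the date of the initial FCM treatment from the date of the further FCM treatment in Phase III, divides by 7, adds 1 and takes the integer. The result is described by n, median, minimum and maximum.
- **Start date.** SAP 6.1.3 then states "Initial treatment is defined as Day 0 of Phase I for responders in Phase I", with Phase II Day 0 for Phase II responders. SAP 1.2.1 and the protocol synopsis carry the same rule ("Initial treatment is defined as Day 0 of Phase I for Responders in Phase I").
- **Who is a responder.** At the end of Phase I, "all subjects will be defined as either treatment responders or non-responders" (SAP 1.3.1), by criteria that do not mention arm. Responders from either phase go on to Phase III. Protocol 8.2 defines the Phase III Safety Population as all of them, and SAP 6 uses each phase's Safety Population for efficacy.
- **Protocol wording.** Protocol 8.4.1: "Estimate the time from first dose of FCM (Day 0 in either Phase I or Phase II) to time of FCM treatment intervention". Protocol 8.5 starts the clock at the first FCM dose, with no mention of Day 0.

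**The concern.** A Phase I placebo responder received normal saline on Days 0 and 7 and has had no FCM on entering Phase III. If that subject's symptoms worsen and FCM is given, it is a first dose, not a further one. The interval back to Phase I Day 0 says how long a placebo response lasted. Placed in the 6.1.3 summary, it would be reported as duration of FCM effect, which is not what the Phase III objective asks.

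Two programmers could follow SAP 6.1.3 in good faith and report different n, median and range for the Phase III primary endpoint. No planned display would reveal the difference. SAP 2.1 generally gives treatment group for Phase I only, and 6.1.3 adds no split. Elsewhere the SAP names the Phase I arm when it wants later results by arm (6.2.1, 6.2.2, 6.2.7).

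**Working it through.** SAP 6.1.3 states no figure to reproduce. The check is a comparison of the texts, followed by a rough size.

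**1. The two readings, for a placebo responder given FCM in Phase III**

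| Reading | Basis | Start date | Contribution |
|---|---|---|---|
| Literal | Definition sentence in SAP 6.1.3; same rule in SAP 1.2.1 and the synopsis | Phase I Day 0 (saline) | One interval, counted as FCM duration |
| FCM-only | Heading and formula of SAP 6.1.3; protocol 8.5 | None exists | No value |

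Illustration: FCM given exactly 25 weeks (175 days) after Phase I Day 0. The literal reading records 175/7 + 1 = 26 weeks. The FCM-only reading records nothing.

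**2. Can such subjects occur?** Responder status and Phase III entry ignore arm. The ferritin limit for retreatment does not by itself remove placebo subjects: the highest entry limit is below 100 ng/mL (protocol 4.2.1) and the retreatment limit is below 300 ng/mL (protocol 6.6).

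**3. Inputs for size.** Protocol 8.1 and SAP 1.3.3 give 35 per arm and much or very much improved CGI-I rates of 50% (FCM) and 15% (placebo). With these rates the stated power above 85% reproduces: 0.896 by the normal approximation, and by exact enumeration 0.903 uncorrected or 0.852 with continuity correction. The CGI-I rate is only a proxy for responder status, which also counts IRLSS of 10 or less and whether the subject asks for more treatment.

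**4. Placebo share of expected Phase I responders**

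- FCM: 35 × 0.50 = 17.5. Placebo: 35 × 0.15 = 5.25.
- Share: 5.25 / 22.75 = 0.15 / 0.65 = 23%. Under 1:1 allocation this ratio does not depend on the number enrolled.
- Assumed alternatives (FCM/placebo): 60%/10% gives 0.10/0.70 = 14%; 40%/30% gives 0.30/0.70 = 43%.

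**5. Share of Phase III entrants.** Non-responders number 35 − 5.25 = 29.75 on placebo and 35 − 17.5 = 17.5 on FCM. Assume that all of them enter Phase II, with response rates of 30% to 50% after placebo and 0% to 50% after FCM.

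- Lowest rates: 22.75 + 29.75 × 0.30 + 0 = 31.675; share 5.25/31.675 = 16.6%.
- Highest rates: 22.75 + 29.75 × 0.50 + 17.5 × 0.50 = 46.375; share 5.25/46.375 = 11.3%.

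If fewer non-responders enter Phase II, the share moves back towards 23%.

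**6. Chance of at least one placebo responder.** This is 1 − 0.85^n. It gives 99.7% for the planned n = 35, and 96%, 80% and 56% for assumed n = 20, 10 and 5. The smaller sizes matter because SAP 9 reports early termination and does not give the number enrolled.

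**7. Where the arithmetic stops.** SAP 6.1.3 has a value only for subjects given FCM in Phase III. The documents give no retreatment rate in either arm, so neither the share of the summary nor the chance that it contains a placebo responder can be calculated.

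**The case against.** The strongest reply is that SAP 6.1.3 never mentions placebo. Its heading and formula require an FCM date, which a placebo responder lacks, so the definition sentence may only say which Day 0 applies to subjects who have had FCM. Protocol 8.5 supports this, and the SAP is to be read with the protocol. This stands in part: the FCM-only reading is legitimate and may well be what was intended. A reader might infer that the plan definitely counts placebo responders as FCM-treated; the text does not go that far. But the definition sentence does assign all Phase I responders a date, and no sentence takes placebo responders out. Protocol 8.4.1 does not settle it, because it describes the first FCM dose as Day 0 of either phase.

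A second reply is that the supplied protocol carries April 2016 dates, whereas the SAP cites a version dated 4 September 2019. The inconsistency does not depend on the protocol: SAP 1.2.1, 1.3.1 and 6.1.3 show it by themselves.

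A third is that the arm-display rule in SAP 2.1 is only a general one, and table shells are not among the documents. That is fair. The missing split is a gap in the text, not a prohibition.

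**Conclusion.** SAP 6.1.3 contains two incompatible instructions for Phase I placebo responders, and the content of the Phase III primary summary depends on which is followed. The literal one departs from the stated objective.

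The size is limited. About 23% of expected Phase I responders, and about 11% to 17% of Phase III entrants, would be placebo responders. These figures rest on CGI-I rates from patients without IDA used as a proxy, and the second also on assumed Phase II response rates and full entry into Phase II. A reader might take 23% as the contaminated share of the reported duration. The documents do not support that, since the summary covers only retreated subjects and includes Phase II responders. Nor do they support a claim that FCM duration would be overstated: the direction is unknown.

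SAP 6 makes the output descriptive, so no test or power figure changes. With few subjects, though, one or two such values could move a median, minimum or maximum. Severity: minor to should-fix.

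**What to change.** In SAP 6.1.3:

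1. Restrict the FCM-duration summary to subjects who received FCM before Phase III: Phase I FCM responders from Phase I Day 0, and Phase II responders from Phase II Day 0, as the SAP already defines.
2. List any retreated Phase I placebo responders separately, labelled as the time from Phase I Day 0 to first FCM.
3. Align the definition in SAP 1.2.1.

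The cost is a clarifying sentence and a row split on the existing randomised-arm variable. No new data are needed. The FCM-duration group becomes slightly smaller, and after early termination the placebo row may be empty.

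This corrects the start date and the label only. SAP 6.1.3 would still describe only retreated subjects, whereas protocol 8.5 plans a Kaplan-Meier estimate in which "Subjects in Phase III who discontinue the study before requiring treatment intervention will be censored". That is a separate matter. So is the origin for Phase I FCM non-responders who respond in Phase II: the SAP times them from Phase II Day 0, although their first FCM dose was in Phase I.
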